### 1.5. Rationale for a Phase II Study in Elderly Patients with AML or MDS

Nucleoside analogues play an important role in the treatment of leukemias and myelodysplastic syndromes (MDS). Ara-C and fludarabine, both nucleoside analogues, are the two most active drugs in these diseases. Despite the impressive ability of these agents to induce partial or complete responses, leukemias and MDS remain incurable in many patients, especially the elderly. This is because responses are usually not durable and the treatment carries significant toxicities. New effective drugs are required to improve the outcome of these diseases.

Sapacitabine, a rationally designed nucleoside analogue, has a unique mechanism of action and good oral bioavailability. In preclinical studies, it demonstrated significant activity against a wide range of malignancies. In the mouse P388 leukemia model, mice treated with sapacitabine had a survival advantage when compared with mice treated with 5'-DFUR.

In the phase I trial of sapacitabine in advanced leukemias or myelodysplastic syndromes (CYC682-05-04), sapacitabine had a favourable safety profile and promising anti-leukemic activity in patients with relapsed and refractory AML and MDS when administered by two different dosing schedules. The MTD was reached at 375 mg on the 7-day schedule and 475 mg on the 3-day schedule. Among 42 patients with AML, the best responses were complete remissions (CR) or complete remissions without platelet recovery (CRp) in 5 patients (age 58, 59, 66, 82, 86) who have relapsed and/or refractory disease following prior therapies consisting of ara-C, anthracycline, clofarabine, mylotarg, fludarabine and/or bone marrow transplant. In addition, 13 patients had a significant decrease in bone marrow blasts including 5 with blast reduction to 5% or less. Among 3 patients with MDS, the best responses were complete remissions (CR) in 1 patient (age 79) and the other 2 patients (age 75, 73) had a decrease of bone marrow blasts to 5% or less. All 3 MDS patients had failed a prior therapy with azacitidine or decitabine.

The rationale for conducting this study in elderly patients with AML or MDS is to assess the efficacy and safety of 3 dosing schedules in this patient population and to select a better dosing schedule for further clinical development.

#### 1.6. Risks and Benefits to Elderly Patients with AML or MDS

Sapcitabine will be administered orally. The major toxicity is expected to be gastrointestinal

toxicities and myelosuppression which are generally reversible after interruption of drug dosing. Serious adverse events related to myelosuppression include febrile neutropenia, neutropenic sepsis, neutropenic colitis and thrombocytopenia. Common non-hematological toxicities include asthenia, nausea, fever, vomiting, diarrhea, anorexia, and dyspnea, which are generally mild to moderate. It is not known whether sapacitabine is an effective agent in the treatment of elderly patients with AML or MDS which is previously untreated or in first relapse. Alternatives to participating in this trial include receiving chemotherapy of other anti-leukemic agents, e.g., ara-C, anthracyclines, participating in clinical trial of a different investigational drug or receiving best supportive care for pain and other cancer-related symptoms.

### 1.7. Good Clinical Practice and Regulatory Requirements

This study will be conducted in compliance with the protocol, Good Clinical Practice (GCP) as described in the ICH tripartite harmonized guidelines, and applicable regulatory requirements.

#### 2. STUDY OBJECTIVES

The primary objective of Part 1 of this study is to evaluate 1-year survival rate of 3 dosing schedules in elderly patients with previously untreated or first relapsed AML or previously treated MDS; the secondary objectives are to assess the number of patients who have achieved a CR, CRp, PR or CRi or hematological improvement and their corresponding durations, transfusion requirements, number of hospitalized days and safety.

The primary objective of Part 2 of this study is to evaluate the rate of clinical benefit response (CR, CRp, PR, major HI or SD) and the rate of complete response (CR or CRp) in elderly patients with previously untreated AML and significant concomitant medical illnesses defined as having a HCTCI of 2 or higher; the secondary objectives are to assess response duration, transfusion requirements, number of hospitalized days, overall survival, and safety.

The primary objective of Part 3 of this study is to evaluate 1-year survival rate of 3 dosing schedules in elderly patients with previously untreated AML that evolved from MDS after receiving hypomethylating agents for the preceding MDS; the secondary objectives are to assess the rate of clinical benefit response (CR, CRp, PR, major HI or SD) and their corresponding durations, transfusion requirements, number of hospitalized days and safety.

The primary objective of Part 4 of this study is to evaluate 1-year survival rate of 3 dosing schedules in older patients with MDS previously treated with hypomethylating agents; the secondary objectives are to assess the rate of clinical benefit response (CR, CRp, PR, major HI or SD) and their corresponding durations, transfusion requirements, number of hospitalized days and safety.

#### 3. STUDY DESIGN

### 3.1. Overall Study Design and Plan

Part 1: This is an open label, randomized, phase II study. Patients will be entered into two separate strata, AML or MDS, and randomized 1:1:1 to receive one of the following 3 dosing schedules within each stratum:

7-day low dose (Arm A): 200 mg b.i.d. x 7 consecutive days every 4 weeks

7-day high dose (Arm B): 300 mg b.i.d. x 7 consecutive days every 4 weeks

3-day high dose (Arm C): 400 mg b.i.d. x 3 consecutive days per week for 2 weeks every 4 weeks

AML patients will be stratified by previously untreated vs. treated for AML within the AML stratum.

Part 2: This is an open-label, single arm, phase II study. Patients will receive sapacitabine at 300 mg *b.i.d.* x 3 consecutive days per week for 2 weeks every 4 weeks.

Part 3: This is an open label, randomized, phase II study. Patients will be randomized 1:1:1 to receive one of the following 3 dosing schedules and the randomization will be stratified by prior treatment with decitabine for MDS (Yes or No):

Arm D: 200 mg b.i.d. x 7 consecutive days every 4 weeks

Arm E: 300 mg q.d. x 7 consecutive days every 4 weeks

Arm F: 300 mg b.i.d. x 3 consecutive days per week for 2 weeks every 4 weeks

Part 4: Eligible patients will be randomized to receive one of the following 3 dosing schedule and the randomization will be stratified by prior treatment with decitabine for MDS (Yes or No):

Arm G: 200 mg b.i.d. x 7 consecutive days every 4 weeks

Arm H: 300 mg q.d. x 7 consecutive days every 4 weeks

Arm I: 100 mg q.d. x 5 consecutive days per week for 2 weeks every 4 weeks

Treatment will continue until: clinically significant progressive disease; lack of efficacy; unacceptable toxicity; patient withdrawal of consent; investigator's discretion that it is in the best interest of the patient to withdraw; intercurrent illness or changes in patient's condition that renders patient ineligible, or continuing treatment of sapacitabine unsafe, or regular

follow-up impossible; non-compliance with study medication or protocol-required evaluations and follow-up; or termination of the clinical trial by the sponsor.

Patients will be monitored regularly with physical exams and laboratory tests. Bone marrow aspirate and/or biopsy will be performed to assess response to sapacitabine. A post-treatment follow-up visit will be conducted within 4 weeks after the last dose of the study drug or prior to the initiation of new treatment, if possible. The post-treatment follow-up may be conducted by telephone if the patient is unable to return to the clinic.

For Part 1, 3 and 4 of the study, the primary efficacy endpoint will be 1-year survival; for Part 2 of the study, there will be two co-primary efficacy endpoints, the rate of clinical benefit response (CR, CRp, PR, major HI or SD) and the rate of complete response (CR or CRp). Stratifications factors and assumptions for sample size and plans for statistical analysis are described in Section 11.

### 3.2. Rationale for the Study Design and Measures to Reduce Bias

The randomized design is used to ensure that the 3 dosing regimens are evaluated in a similar patient population.

### 3.3. Rationale for the Proposed Dosing Schedules

Preliminary pharmacokinetic analyses from two completed phase I studies indicate that sapacitabine and its active metabolite CNDAC have a relatively short half-life (approximately 2 hours) and that CNDAC exposure appears to correlate with the worst NCI-CTC grade of neutropenia experienced during treatment at the MTD. We hypothesize that the 7-day high dose regimen will lead to higher dose delivered per week (1400 mg/week) resulting in better antitumor activity than the 7-day low dose regimen (933 mg/week) but may cause more myelosuppression; the 3-day high dose regimen will have higher dose delivered per week (1600 mg/week) resulting in better anti-tumor activity than the 7-day high dose regimen but will have similar degree of myelosuppression and gastrointestinal toxicity because the consecutive days of dosing are shorter. Preliminary data from the 60 patients in the original cohort of the AML stratum showed that the dosing schedule of 400 mg b.i.d. x 3 days/week x 2 weeks every 3-4 weeks has the highest rate of CR/CRp, i.e., 25%, the longest durations of responses, and a 10% all-cause death rate within the first 30 days after randomization. However, all patients who achieved CRs were dose reduced for myelosuppression. We hypothesize that a 3-day dosing regimen of 300 mg b.i.d. x 3 days/week x 2 weeks every 4 weeks will be equally effective but with less myelosuppression and propose to test this dosing regimen in Part 2 of the study. Exploratory subgroup analyses from AML patients enrolled in Part 1 of the study suggest that the 7-day low dose schedule of 200 mg b.i.d. x 7 days every 3-4 weeks (Arm A) may be more effective for AML preceded by MDS or MPD. Among 7 patients on Arm A who have survived at least 1 year, 4 patients have AML preceded by MDS or MPD. We hypothesize that a 7-day once daily (q.d.) dose regimen and a lower dose of the 3-day dose regimen may be equally effective but with less myelosuppression. We propose to evaluate 300 mg a.d. x 7 days and 300 mg b.i.d.

x 3 days/week x 2 weeks every 4 weeks in patients with newly diagnosed AML preceded by MDS after receiving hypomethylating agents for the preceding MDS (Part 3).

Interim data from MDS patients enrolled in Part 1 of the study showed that most of the responses occurred on the 7-day low dose and high dose regimens. We hypothesize that a 7-day once daily (*q.d.*) dose regimen may be equally effective but with less myelosuppression. In addition, we propose to evaluate a new dose regimen i.e.100 mg *q.d.* x 5 days/week x 2 weeks every 4 weeks. This 5-day dose regimen appears to be well tolerated in patients with lung cancer (study CYC682-8). We hypothesize that this increase in exposure may lead to further improvement in efficacy in patients with MDS that was previously treated with hypomethylating agents (Part 4).

### 3.4. Study Duration

Approximately 100 patients with AML and 60 patients with MDS will be enrolled in Part 1 of this study. Approximately 36 patients with AML will be enrolled in Part 2 of the study. Approximately 60 patients with AML preceded by MDS and 60 patients with MDS will be enrolled in Part 3 and Part 4 of this study, respectively. The patient accrual is projected to be 8 patients per month for approximately 41 months. The study may be closed approximately 6 months after the last patient was enrolled, thus the projected entire study duration is 47 months. After study closure, all patients who are deriving clinical benefit and continue to meet the eligibility criteria may be offered the option to continue treatment on an extension study.

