schedule:  Arm G: 200 mg b.i.d. x 7 consecutive days every 4 weeks  Arm H: 300 mg q.d. x 7 consecutive days every 4 weeks	s
Arm H: 300 mg q.d. x 7 consecutive days every 4 weeks	
Arm I: 100 mg a d v 5 consecutive days per week for 2 weeks every 4 weeks	
Min 1. 100 mg q.a. x 3 consecutive days per week for 2 weeks every 4 weeks	
Treatment will continue until: clinically significant progressive disease; lack of efficacy; unacceptable toxicity; patient withdrawal of consent; investigator's discretion that it is in the best interest of the patient to withdraw; intercurrent illnes or changes in patient's condition that renders patient ineligible, or continuing treatment of sapacitabine unsafe, or regular follow-up impossible; non-compliance with study medication or protocol-required evaluations and follow-up; or termination of the clinical trial by the sponsor.	
Efficacy Assessment  The primary efficacy endpoint of Part 1, 3 and 4 is the rate of 1-year survival; the primary efficacy endpoints of Part 2 are the rate of clinical benefit (CR, CRp, PR major HI or SD) and the rate of complete response (CR or CRp).	
Safety Assessment  Patients will be seen in the clinic prior to each treatment cycle and monitored by physical exams, laboratory tests, and other appropriate studies. A post-treatment follow-up visit in clinic or by phone will be conducted within 4 weeks after the las dose of the study drug, or prior to the initiation of new cancer treatment if possible	
Study Period December 2007 to November 2011	

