### 6.4. Post-Treatment Follow-up

All patients should be followed regularly until the resolution or stabilization of drug-related toxicity or the start of another anti-cancer treatment. Every effort will be made to conduct a post-treatment follow-up visit within 4 weeks after the last dose of the study drug or prior to the initiation of new treatment, whichever comes first. This post-treatment evaluation may be conducted over the telephone if the patient is unable to return to the clinic.

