g: These evaluations on Day 1 Cycle 1 may not need to be performed if the same evaluations performed during Pre-Study period are within 7 days of the first dose of the study drug; physical exam in clinic may be waived every 1-2 cycles at the investigator's discretion after cycle 6.

h: To be performed prior to the start of cycle 2 on patients who have >5% blasts in bone marrow, i.e., during Day -21-28 of Cycle 1 which may be delayed up to Day 35 for recovery of blood counts; as clinically indicated after subsequent cycles e.g., at the time when blood counts have recovered or worsened.

i: Within 28 days after the last dose of study drug if possible or prior to the initiation of new anticancer treatment, whichever comes first.

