### 8.2. Serious Adverse Event Reporting

A serious adverse event is defined as an untoward (unfavorable) medical occurrence that at any dose:

- Results in death
- Is life-threatening. The term "life-threatening" refers to an event in which the patient was at risk of death at the time of the event; it does not refer to an event which hypothetically might have caused death if it were more severe.
- Requires inpatient hospitalization or prolongation of existing hospitalization
- Results in persistent or significant disability/incapacity
- Is a congenital anomaly/birth defect
- Jeopardizes the subject/patient and may require medical or surgical intervention to prevent one of the outcomes listed above

Important medical events that do not result in death, are not life-threatening, or do not require hospitalization could be considered SAEs when, based upon appropriate medical judgment, they jeopardize the subject, or require medical or surgical intervention to prevent any of the outcomes listed above. Examples of such medical events include allergic bronchospasm requiring intensive treatment in an emergency room or at home, blood dyscrasias or convulsions that do not require hospitalization, or development of drug dependency or drug abuse.

Any SAE or death that occurs after study drug administration through 28 days from the last dose of study drug or until the initiation of a new anticancer therapy, whichever comes first, must be reported to Theradex® immediately via telephone or FAX within 24 hours of the first

knowledge of the occurrence of the event. In addition, any SAE and death that occurs while a patient is not receiving the study drug but remains on study, must also be reported to Theradex as described above.

- For this study, myelosuppression and its associated complications due to underlying leukemia and/or anti-leukemia therapy are expected events during therapy. Hospitalizations for the treatment of the following events that are known to be associated with myelosuppression from leukemia and/or study drug are not required to be reported to Theradex® but still need to be captured as SAEs on the case report form :
  - o Fatigue, weakness and/or shortness of breath associated with anemia
  - o Febrile neutropenia
  - Mucosal bleeding due to thrombocytopenia e.g., epistaxis, gastrointestinal bleeding
  - o Bacteremia, sepsis, pneumonia, cellulitis, neutropenic colitis

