#### 9. EFFICACY ASSESSMENT

The primary efficacy endpoint of Part 1 of this study is 1-year survival, i.e., the proportion of patients who are alive at 1-year measured from the date of the randomization. Secondary efficacy endpoints are the rate of CR, CRp, PR or CRi or hematological improvement and their corresponding durations, transfusion requirements and number of hospitalized days. The primary efficacy endpoints of Part 2 of this study are the rate of clinical benefit response (CR, CRp, PR, or major HI) and the rate of complete response (CR or CRp). Secondary efficacy endpoints are response durations, transfusion requirements, number of hospitalized days, and overall survival. The primary efficacy endpoint of Part 3 and 4 of this study is 1-year survival rate. Secondary efficacy endpoints are the rate of clinical benefit response (CR, CRp, PR, major HI or SD) and their corresponding durations, transfusion requirements, number of hospitalized days and overall survival.

The tissue samples supporting the diagnosis of AML or MDS, and the responses to sapacitabine may be submitted for central review.

Table 6 Response Criteria

Passansa Description					
Response	Description				
Complete Remission (CR) 	Normalization of peripheral neutrophils to ≥1000 /µL, platelet to ≥100,000/µL within 2 weeks of bone marrow biopsy/aspirate, and bone marrow to ≤5 % blasts; independent of transfusions*; and no extramedullary leukemia.				
Complete remission with incomplete platelet count recovery (CRp) 	Normalization of bone marrow to $\leq$ 5% blasts; peripheral neutrophils $\geq$ 1000 /µl, platelet $<$ 100,000 /µL within 2 weeks of bone marrow biopsy/aspirate; independent of transfusions*; and no extramedullary leukemia.				
Complete remission with incomplete blood count recovery (CRi) 8	Normalization of bone marrow to $\leq$ 5% blasts; peripheral neutrophils $<1000~/\mu$ L, platelet $<100,000/\mu$ L within 2 weeks of bone marrow biopsy/aspirate; independent of transfusions *; and no extramedullary leukemia.				
Partial Remission (PR) 8	Normalization of peripheral neutrophils to $\geq 1000 \ / \mu L$ , platelet to $\geq 100,000/\mu L$ within 2 weeks of bone marrow biopsy/aspirate, $\geq 50\%$ decrease in bone marrow blasts over pretreatment but still >5%; independent of transfusions * .				
Hematological improvement (HI) 9	Major response:				

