#### 11.3.2. Selection Design

Assuming that at least 2 dosing schedules show activity and that their toxicity profile is similar, a selection design will be used to choose the dosing schedule with the better observed 1-year survival rate. If the better dosing schedule has a true 1-year rate of 45% and the worse dosing schedule a true 1-year rate of 30%, the trial has better than 80% probability to choose the correct dosing schedule if 20 patients have been treated with each dosing schedule.

No formal hypothesis testing will be carried out for the 1-year survival rate. Instead, we will estimate the 1-year survival rate for each dosing schedule, along with the 95% confidence interval. Given a total of 20 patients in an arm and assuming a 1-year survival rate of 45%, the half-width of the 95% confidence interval will be 0.22. On the other hand, if assuming a 1-year survival rate of 30%, the half-width of the 95% confidence interval will be 0.20.

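### The plan does not secure 1-year vital status for all randomized patients in Parts 1, 3 and 4, although 1-year survival is their primary endpoint and selects the dosing schedule

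*Combined protocol and SAP*

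**What the plan says.** **Endpoint and use.** Section 9 defines the Part 1 primary endpoint as "1-year survival, i.e., the proportion of patients who are alive at 1-year measured from the date of the randomization"; Section 11.3 gives Parts 3 and 4 the same endpoint, measured from randomization. In Sections 11.1.2 and 11.3.2, "a selection design will be used to choose the dosing schedule with the better observed 1-year survival rate". Section 11.4 makes all randomized patients the primary analysis population.

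**Closure.** Section 3.4 projects 8 patients a month for about 41 months and adds: "The study may be closed approximately 6 months after the last patient was enrolled". The 47-month duration is 41 + 6. The synopsis gives "Study Period December 2007 to November 2011", which fits that figure.

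**Follow-up.** Section 6.4: "All patients should be followed regularly until the resolution or stabilization of drug-related toxicity or the start of another anti-cancer treatment". The last contact in Table 5 is the post-treatment visit, which footnote i times as "Within 28 days after the last dose of study drug if possible or prior to the initiation of new anticancer treatment, whichever comes first". Section 8.2 requires reporting of "Any SAE or death that occurs after study drug administration through 28 days from the last dose of study drug", or until new anticancer therapy if that comes first. It goes further only for a patient off drug who is still on study, and no duration is given for that state.

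**Analysis.** Section 11.4 includes overall survival among the quantities estimated by Kaplan-Meier. The sentence after it censors patients who leave the study for reasons other than progression at their last response evaluation, and does not exempt survival.

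**The concern.** A proportion alive at 1 year, taken over all randomized patients, needs each patient's vital status at 12 months. The plan falls short in four places:

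1. The earliest planned closure comes before late entrants reach 12 months.
2. No survival contact is scheduled once a patient is off treatment, whenever the study closes.
3. The only censoring rule is tied to response evaluation. If it were applied to survival, deaths known to have occurred later would be dropped, censoring would be informative, and survival would be biased upward.
4. No passage says whether an unknown patient counts as dead, counts as alive or is left out.

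The late entrants probably sit mostly in Parts 3 and 4, because Section 3.3 justifies those Parts with Part 1 results (for Part 4: "Interim data from MDS patients enrolled in Part 1 of the study showed"). The choice of schedule in each Part rests on arms of about 20, so a few unknowns per arm matter.

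**Working it through.** **The plan's own figures.**
- Accrual: 8 × 41 = 328, against about 325. Duration: 41 + 6 = 47 months.
- Half-width, 1.96 × √(p(1−p)/20): 0.218 at p = 0.45 and 0.201 at p = 0.30, matching the stated 0.22 and 0.20.
- Correct selection between two arms of 20 at 45% and 30%, exact binomial with ties split: 0.836, matching the stated figure of better than 80%.

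All of these assume that 1-year status is known for all 20 patients per arm.

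**Late entrants.** 8 × (12 − 6) = 48 patients; 48/325 = 14.8%. Part 2 has response endpoints. Pro rata on the Section 3.4 part sizes (280 of 316), about 48 × 280/316 = 43 fall in Parts 1, 3 and 4.

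**Unknown 1-year status per arm, from closure alone.** Assume exponential survival with S(12) = 0.45 or 0.30 and uniform accrual over A months. A late entrant is unknown only if alive at closure, so

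unknown = 20 × ∫₆¹² S(u) du / A.

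The integral is 3.318 at 45% and 2.469 at 30%. Two accrual assumptions bracket the answer: late entrants spread evenly (A = 41), or Parts 3 and 4 enrolling last and alone (A = 120/8 = 15).

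| True rate | A = 41 | A = 15 |
|---|---|---|
| 45% | 1.62 | 4.42 |
| 30% | 1.20 | 3.29 |

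**Effect on a simple proportion.** With A = 15, 20 × 6/15 = 8 patients per arm are late and 12 are fully followed. At 45%, 12 × 0.45 = 5.4 are known alive:
- unknowns counted as not alive: 5.4/20 = 0.27
- unknowns excluded: 5.4/(20 − 4.42) = 0.35
- unknowns counted as alive: (5.4 + 4.42)/20 = 0.49

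At 30%, 12 × 0.30 = 3.6 are known alive, and the same steps with 3.29 unknown give 0.18, 0.22 and 0.34. With A = 41, the readings are 0.38, 0.42 and 0.47 for a true 0.45, and 0.26, 0.27 and 0.32 for a true 0.30.

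**Effect with Kaplan-Meier.** The Greenwood variance with n = 20 and G(u) = 1 − (u − 6)/A after month 6 gives these half-widths:

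| True rate | Full follow-up | A = 41 | A = 15 |
|---|---|---|---|
| 45% | 0.218 | 0.224 | 0.237 |
| 30% | 0.201 | 0.207 | 0.220 |

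Simulated two-arm correct selection (100,000 runs, A = 15) is about 0.82, against 0.836 with full follow-up.

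**Not quantified.** Loss of contact after treatment and any bias from the censoring rule depend on discontinuation rates that the documents do not give.

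**The case against.** The closure wording is permissive. With Kaplan-Meier, correct selection stays above 80%: about 0.82 if Parts 3 and 4 enrol last, 0.83 with even accrual. The most striking readings need an enrolment order that no passage states, and also a counting rule that no passage prescribes. Even with unknowns counted as not alive, even accrual keeps selection at about 0.81; it falls to about 0.75 only when that rule is combined with late, separate enrolment of Parts 3 and 4. The censoring sentence speaks of progression and response evaluation, so it may be meant only for response durations. The sponsor clearly intends to collect survival: overall survival is listed as an efficacy and safety measure, and Section 3.3 reports seven Arm A patients who lived at least 1 year. The Operations Manual, which is not available here, may say more.

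Most of this stands as a limit on the closure and censoring points. Closure alone would be a modest problem, and the censoring sentence mainly needs clarifying. None of it supplies the missing follow-up. Survival of at least 1 year in some patients does not show that status is required for all. The protocol refers to the Operations Manual for other procedures, but not for survival follow-up. The plan also defines a proportion and does not prescribe Kaplan-Meier for the 1-year rate, so the protection that estimator gives is not assured.

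**Conclusion.** The concern holds and must be fixed. As written, the plan does not assure the primary endpoint for late entrants or for patients who are off treatment before 1 year.

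The follow-up gap is the most serious part: it affects all three Parts, does not depend on the closure date, and cannot be sized from the documents. Closure at 6 months puts about 48 patients (15%) under 12 months of potential follow-up. Under exponential survival at the plan's 30% to 45% rates, it leaves about 1.2 to 1.6 unknown per arm of 20 with even accrual, or 3.3 to 4.4 if Parts 3 and 4 enrol last and alone. In the latter case the counting rule alone moves a true 45% between 27% and 49%, a spread wider than the 15-point difference the selection design targets. With Kaplan-Meier and administrative censoring, closure costs only 0.02 in half-width and about 0.02 in selection probability. Whether the Section 11.4 censoring rule reaches survival is unclear from the text.

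**What to change.** - **Section 3.4 and synopsis.** For Parts 1, 3 and 4, close no earlier than 12 months after the last randomization: 41 + 12 = 53 months, with the study period running to about May 2012.
- **Section 6.4 and Table 5.** Collect vital status by telephone through at least 12 months from randomization for every randomized patient, regardless of treatment discontinuation or new therapy. State how patients who withdraw from the study altogether are handled.
- **Section 11.4.** For overall and 1-year survival, count death from any cause as an event and censor only at the date last known alive. Estimate the 1-year rate by Kaplan-Meier whenever any 1-year status is unknown. State that the last-response-evaluation rule applies to response durations only.

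The cost is amendment wording, about 6 more months of study, and telephone calls to off-treatment patients in three Parts for as long as those Parts run. No extra patients or clinic procedures are needed.
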